4.5.10.7 Withdrawal from the Research Biosample Repository

Patients who give consent to provide RBR specimens have the right to withdraw their specimens from the RBR at any time for any reason. After withdrawal of consent, any remaining samples will be destroyed or will no longer be linked to the patient. However, if RBR samples have been tested prior to withdrawal of consent, results from those tests will remain as part of the overall research data. If a patient wishes to withdraw consent to the testing of his or her specimens, the investigator must inform the Medical Monitor in writing of the patient's wishes through use of the appropriate RBR Subject Withdrawal Form and, if the trial is ongoing, must enter the date of withdrawal on the RBR Research Sample Withdrawal of Informed Consent eCRF. If a patient wishes to withdraw consent to the testing of his or her RBR samples after closure of the site, the investigator must inform the Sponsor by emailing the study number and patient number to the following email address:

[contact]

The patient will be provided with instructions on how to withdraw consent after the trial is closed. A patient's withdrawal from Study MO39171 does not, by itself, constitute withdrawal of specimens from the RBR. Likewise, a patient's withdrawal from the RBR does not constitute withdrawal from Study MO39171.

4.5.10.8 Monitoring and Oversight

RBR specimens will be tracked in a manner consistent with Good Clinical Practice by a quality-controlled, auditable, and appropriately validated laboratory information management system, to ensure compliance with data confidentiality as well as adherence to authorized use of specimens as specified in this protocol and in the Informed Consent Form. Sponsor monitors and auditors will have direct access to appropriate parts of records relating to patient participation in the RBR for the purposes of verifying the data provided to the Sponsor. The site will permit monitoring, audits, IRB/EC review, and health authority inspections by providing direct access to source data and documents related to the RBR samples.

4.6 PATIENT, TREATMENT, STUDY, AND SITE DISCONTINUATION

4.6.1 Patient Discontinuation

Patients have the right to voluntarily withdraw from the study at any time for any reason. In addition, the investigator has the right to withdraw a patient from the study at any time. Reasons for withdrawal from the study may include, but are not limited to, the following:

- Patient withdrawal of consent at any time
- Any medical condition that the investigator or Sponsor determines may jeopardize the patient's safety if he or she continues in the study
- Investigator or Sponsor determines it is in the best interest of the patient
- Patient non-compliance

Every effort should be made to obtain information on patients who withdraw from the study. The primary reason for withdrawal from the study should be documented on the appropriate eCRF. Subjects who discontinue will be asked to provide consent allowing the Study Investigator and/or F. Hoffman-La Roche Ltd to collect follow up information regarding disease progression and survival. Otherwise, without this consent, patients will not be followed for any reason after withdrawal. Patients who withdraw from the study will not be replaced.

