4.6.2 Study Treatment Discontinuation

Patients must discontinue study treatment (but will continue to receive tumor assessments) if they experience any of the following:

- Intolerable toxicity related to study treatment
- Myocarditis of any grade
- Any medical condition that may jeopardize the patient's safety if he or she continues on study treatment
- Use of another systemic anti-cancer therapy (see Section [4.4.2](#))
- Pregnancy
- Radiographic disease progression per RECIST v1.1

[figure not shown]
Exception: Patients will be permitted to continue atezolizumab after RECIST v1.1 criteria for progressive disease are met if they meet all of the following criteria (see [Figure 3](#) for schematic representation):

- Evidence of clinical benefit (defined as the stabilization or improvement of disease-related symptoms) as assessed by the investigator
- Absence of symptoms and signs (including worsening of laboratory values [e.g., new or worsening hypercalcemia]) indicating unequivocal progression of disease
- No decline in ECOG performance status that can be attributed to disease progression
- Absence of tumor progression at critical anatomical sites (e.g., leptomeningeal disease) that cannot be readily managed and stabilized by protocol-allowed medical interventions prior to repeat dosing

Patients who demonstrate confirmed radiographic disease progression may be considered for continued study treatment at the discretion of the investigator, provided they continue to meet all the criteria above

The primary reason for study treatment discontinuation should be documented on the appropriate eCRF. Patients who discontinue study treatment prematurely will not be replaced.

Figure 3 Conditions for Continuing Atezolizumab in the Presence of Increased Radiographic Tumor Size

ECOG PS, Eastern Cooperative Oncology Group performance status; ICF, Informed Consent Form; RECIST v1.1, Response Evaluation Criteria in Solid Tumors, Version 1.1.

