5.3.1 Adverse Event Reporting Period

Investigators will seek information on adverse events at each patient contact. All adverse events, whether reported by the patient or noted by study personnel, will be recorded in the patient's medical record and on the Adverse Event eCRF.

After informed consent has been obtained **but prior to initiation of study drug**, only serious adverse events caused by a protocol-mandated intervention (e.g., invasive procedures such as biopsies, discontinuation of medications) should be reported (see Section 5.4.2 for instructions for reporting serious adverse events).

After initiation of study drug, all adverse events will be reported until 30 days after the last dose of study drug and 90 days for serious adverse events or adverse events of special interest.

Instructions for reporting adverse events that occur after the adverse event reporting period are provided in Section 5.6.

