5.5 FOLLOW-UP OF PATIENTS AFTER ADVERSE EVENTS

5.5.1 Investigator Follow-Up

The investigator should follow each adverse event until the event has resolved to baseline grade or better, the event is assessed as stable by the investigator, the patient is lost to follow-up, or the patient withdraws consent. Every effort should be made to follow all serious adverse events considered to be related to study drug or trial-related procedures until a final outcome can be reported.

During the study period, resolution of adverse events (with dates) should be documented on the Adverse Event eCRF and in the patient's medical record to facilitate source data verification.

All pregnancies reported during the study should be followed until pregnancy outcome.

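### Section 4.6.1 limits follow-up after study withdrawal to progression and survival, or to nothing, which contradicts the 90-day SAE/AESI reporting rule and can lower the primary safety incidences

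*Protocol*

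**What the plan says.** Protocol Section 4.6.1 (Patient Discontinuation) states that "the investigator has the right to withdraw a patient from the study at any time". Its list of reasons, which is not exhaustive, includes "Any medical condition that the investigator or Sponsor determines may jeopardize the patient's safety if he or she continues in the study", the patient's best interest as judged by the investigator or Sponsor, and non-compliance. The section asks sites to make every effort to obtain information on patients who withdraw. It then defines the consent sought from those who discontinue, and what follows without it: permission to "collect follow up information regarding disease progression and survival. Otherwise, without this consent, patients will not be followed for any reason after withdrawal".

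Section 4.6.2 (Study Treatment Discontinuation) has a separate list of reasons to stop treatment while tumor assessments continue. It includes intolerable treatment-related toxicity and "Any medical condition that may jeopardize the patient's safety if he or she continues on study treatment".

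On safety reporting, Section 5.3.1 says that after study drug starts "all adverse events will be reported until 30 days after the last dose of study drug and 90 days for serious adverse events", and the sentence goes on to include AESIs. Section 5.4.2.2 repeats this. Appendix 1 note x has the same windows, ending earlier if new anti-cancer therapy begins. None of the three makes an exception for a patient withdrawn from the study. Section 5.5.1 says "The investigator should follow each adverse event until the event has resolved to baseline grade or better"; the other end points it lists are a stable event, loss to follow-up and withdrawal of consent by the patient.

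**The concern.** Safety is the primary objective. The two primary endpoints are the incidences of related SAEs and of related irAEs, yet the only consent sought after withdrawal covers efficacy information. A patient whom the investigator or Sponsor removes has not withdrawn consent. Sections 5.3.1 and 5.5.1 still require that patient's safety follow-up, while 4.6.1, read literally, forbids it unless a further consent is given and leaves safety out even then. Two sites could treat identical patients differently, and both could cite the protocol.

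At stake is the completeness of the numerator for the primary endpoints. The SAP's long-term safety table (SAP 3.5.5), which concerns SAEs and AESIs recorded after the 30-day point, depends on the same reporting window. Survival is affected too: a patient who does not give the consent is censored when last known alive, which bears on the 2-year OS rate, the main secondary endpoint.

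**Working it through.** **The texts side by side, for a patient withdrawn by the investigator who has not withdrawn consent**

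- Section 4.6.1, further consent given: progression and survival are collected; safety is not mentioned.
- Section 4.6.1, further consent not given: no follow-up of any kind.
- Sections 5.3.1 and 5.4.2.2, and Appendix 1 note x: AEs to 30 days and SAEs/AESIs to 90 days after the last dose.
- Section 5.5.1: recorded AEs are followed until resolved or stable. The withdrawal-of-consent stop does not apply, because the patient did not withdraw it.
- Section 5.6: after the reporting period, related SAEs are reported if the investigator becomes aware of them. Note x extends this to related AESIs. Both are passive.

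Without the further consent, the 4.6.1 rule and the Section 5 rules cannot both be followed. With it, 4.6.1 is silent on safety and Section 5 requires safety reporting. No text says which section prevails.

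**How a missed event enters the analysis**

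1. Denominator: all patients given any dose (Protocol 6.4, SAP 3.1.1). Withdrawn patients remain in it and are not replaced (4.6.1).
2. Estimator: crude incidence with a Clopper-Pearson interval (Protocol 6.4, SAP 3.5.2).
3. Missing data: SAP 3.6 deals with partial or missing dates. It has no rule for safety follow-up cut short by withdrawal.
4. Let *E* be the number of patients with a qualifying event and *m* the number whose first qualifying event falls after withdrawal and is not captured. The observed incidence is (*E* − *m*)/*N*, so the error is −*m*/*N*, which is zero or negative.
5. With *N* = 600, each missed patient costs 1/600 = 0.17 percentage points.

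**Scale.** The plan gives no figure for withdrawal. The only yardstick is its precision table (Protocol Table 12), which prints 7.6% to 12.4% for a 10% incidence. The normal approximation reproduces this: 10% ± 1.96 × √(0.10 × 0.90/600) = 10% ± 2.4 points. The exact method named in the table gives 7.72% to 12.68%; that mismatch is a separate matter. A shift of 2.4 points corresponds to 0.024 × 600 = 14.4, so about 15 missed patients would match the printed half-width. Whether *m* is near 0 or near 15 cannot be told. It depends on how many patients are withdrawn, how many of them had no earlier qualifying event, how many then have one, and how many of those escape Sections 5.3.1 and 5.6. The documents give none of these.

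**Overall survival.** Under SAP 3.4.1.1 a patient not known to have died is censored when last known alive. If patients who refuse the consent have a worse prognosis than those still followed, the Kaplan-Meier rate is too high; if their prognosis is similar, only precision is lost. The documents do not say which applies.

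**The case against.** The best defense is that this is a wording conflict and not a decision to discard safety data. Much of that stands.

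- Section 5 requires 30- and 90-day reporting for everyone dosed, and 4.6.1 itself asks for every effort to obtain information. A reader might infer that post-withdrawal safety data are definitely not collected. The documents contradict each other on this; they do not settle it. The consent form is not in the public documents and may already allow safety follow-up.
- A reader might infer that toxicity is a listed reason for leaving the study. It is not. Intolerable toxicity is in 4.6.2, where only treatment stops. The medical-condition reason in 4.6.1 could be applied to a toxicity case, but that is an inference from similar wording.
- A reader might infer that events are lost mainly in the patients at highest risk. The endpoints count patients, so anyone withdrawn after a qualifying event is already counted for that endpoint. Only a first qualifying event after withdrawal is exposed, and Section 5.6 and note x may still catch some.
- The irAE definition needs systemic corticosteroid use within 30 days of onset. A reader might blame 4.6.1 for missing steroid data. Section 4.4 ends concomitant-medication collection at the treatment discontinuation visit for every patient, so that is a separate issue.

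The conflict itself remains. Passive reporting does not replace active follow-up inside the 90-day window, and nothing in the protocol tells a site to set aside the explicit sentence in 4.6.1.

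**Conclusion.** The point holds as an internal contradiction with a possible effect on the primary endpoints. Section 4.6.1 states a follow-up rule that conflicts with Sections 5.3.1, 5.4.2.2 and 5.5.1 and Appendix 1 note x. If a site applies it, first related SAEs or irAEs after withdrawal can be missed, and the crude incidences then treat those patients as event-free. The direction is downward and the size is unknown. The documents do not support any estimate of events lost or of survival bias, nor the claim that the loss is concentrated in patients withdrawn for toxicity. The conclusion assumes only that some patients are withdrawn by the investigator or Sponsor without withdrawing consent, and that some sites would follow 4.6.1 as written. Because safety is the primary objective and the correction is small, it should be made.

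**What to change.** (a) In 4.6.1, restrict the no-follow-up sentence to patients who themselves withdraw consent. Patients withdrawn by the investigator or Sponsor then keep SAE/AESI reporting to 90 days after the last dose, and survival follow-up.

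(b) Add SAEs and AESIs to 90 days after the last dose to the follow-up consent request, alongside progression and survival.

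(c) Reconcile the near-identical medical-condition reasons in 4.6.1 and 4.6.2, so that a site can tell when a patient leaves treatment and when a patient leaves the study. Which clinical rule applies is for the sponsor to decide; the two passages need only agree.

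Cost: amendment wording, one sentence in the consent form and a few extra site contacts. No visits are added.

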4.6.2 Study Treatment Discontinuation

Patients must discontinue study treatment (but will continue to receive tumor assessments) if they experience any of the following:

- Intolerable toxicity related to study treatment
- Myocarditis of any grade
- Any medical condition that may jeopardize the patient's safety if he or she continues on study treatment
- Use of another systemic anti-cancer therapy (see Section [4.4.2](#))
- Pregnancy
- Radiographic disease progression per RECIST v1.1

[figure not shown]
Exception: Patients will be permitted to continue atezolizumab after RECIST v1.1 criteria for progressive disease are met if they meet all of the following criteria (see [Figure 3](#) for schematic representation):

- Evidence of clinical benefit (defined as the stabilization or improvement of disease-related symptoms) as assessed by the investigator
- Absence of symptoms and signs (including worsening of laboratory values [e.g., new or worsening hypercalcemia]) indicating unequivocal progression of disease
- No decline in ECOG performance status that can be attributed to disease progression
- Absence of tumor progression at critical anatomical sites (e.g., leptomeningeal disease) that cannot be readily managed and stabilized by protocol-allowed medical interventions prior to repeat dosing

Patients who demonstrate confirmed radiographic disease progression may be considered for continued study treatment at the discretion of the investigator, provided they continue to meet all the criteria above

The primary reason for study treatment discontinuation should be documented on the appropriate eCRF. Patients who discontinue study treatment prematurely will not be replaced.

Figure 3 Conditions for Continuing Atezolizumab in the Presence of Increased Radiographic Tumor Size

ECOG PS, Eastern Cooperative Oncology Group performance status; ICF, Informed Consent Form; RECIST v1.1, Response Evaluation Criteria in Solid Tumors, Version 1.1.

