Immune-related myocarditis has been associated with the administration of atezolizumab. Immune-related myocarditis should be suspected in any patient presenting with signs or symptoms suggestive of myocarditis, including, but not limited to, laboratory (e.g., B-type natriuretic peptide) or cardiac imaging abnormalities, dyspnea, chest pain, palpitations, fatigue, decreased exercise tolerance, or syncope. Immune-related myocarditis needs to be distinguished from myocarditis resulting from infection (commonly viral, e.g., in a patient who reports a recent history of gastrointestinal illness), ischemic events, underlying arrhythmias, exacerbation of preexisting cardiac conditions, or progression of malignancy.

All patients with possible myocarditis should be urgently evaluated by performing cardiac enzyme assessment, an ECG, a chest X-ray, an echocardiogram, and a cardiac MRI as appropriate per institutional guidelines. A cardiologist should be consulted. An endomyocardial biopsy may be considered to enable a definitive diagnosis and appropriate treatment, if clinically indicated.

Patients with signs and symptoms of myocarditis, in the absence of an identified alternate etiology, should be treated according to the guidelines in [Table 6](#).

Table 6 Management Guidelines for Immune-Related Myocarditis

Event	Management
Immune-related myocarditis, Grade 2	
 Withhold atezolizumab for up to 12 weeks after event onset^a and contact Medical Monitor. Refer patient to cardiologist. Initiate treatment as per institutional guidelines and consider antiarrhythmic drugs, temporary pacemaker, ECMO, or VAD as appropriate. Consider treatment with corticosteroids equivalent to 1–2 mg/kg/day IV methylprednisolone and convert to 1–2 mg/kg/day oral prednisone or equivalent upon improvement. If event resolves to Grade 1 or better, resume atezolizumab.^b If event does not resolve to Grade 1 or better while withholding atezolizumab, permanently discontinue atezolizumab and contact Medical Monitor.^c

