Immune-related myocarditis, Grade 3-4	
 Permanently discontinue atezolizumab and contact Medical Monitor.^c Refer patient to cardiologist. Initiate treatment as per institutional guidelines and consider antiarrhythmic drugs, temporary pacemaker, ECMO, or VAD as appropriate. Initiate treatment with corticosteroids equivalent to 1–2 mg/kg/day IV methylprednisolone and convert to 1–2 mg/kg/day oral prednisone or equivalent upon improvement. If event does not improve within 48 hours after initiating corticosteroids, consider adding an immunosuppressive agent. If event resolves to Grade 1 or better, taper corticosteroids over \geq 1 month.

ECMO=extracorporeal membrane oxygenation; VAD=ventricular assist device.

^a Atezolizumab may be withheld for a longer period of time (i.e., $>$ 12 weeks after event onset) to allow for corticosteroids (if initiated) to be reduced to the equivalent of \leq 10 mg/day oral prednisone. The acceptable length of the extended period of time must be agreed upon by the investigator and the Medical Monitor.

^b If corticosteroids have been initiated, they must be tapered over \geq 1 month to the equivalent of \leq 10 mg/day oral prednisone before atezolizumab can be resumed.

^c Resumption of atezolizumab may be considered in patients who are deriving benefit and have fully recovered from the event. Patients can be re-challenged with atezolizumab only after approval has been documented by both the investigator (or an appropriate delegate) and the Medical Monitor.

INFUSION-RELATED REACTIONS AND CYTOKINE-RELEASE SYNDROME

No premedication is indicated for the administration of Cycle 1 of atezolizumab. However, patients who experience an infusion-related reaction (IRR) or cytokine-release syndrome (CRS) with atezolizumab may receive premedication with antihistamines, anti-pyretics, and/or analgesics (e.g., acetaminophen) for subsequent infusions. Metamizole

(dipyrone) is prohibited in treating atezolizumab-associated IRRs because of its potential for causing agranulocytosis.

IRRs are known to occur with the administration of monoclonal antibodies and have been reported with atezolizumab. These reactions, which are thought to be due to release of cytokines and/or other chemical mediators, occur within 24 hours of atezolizumab administration and are generally mild to moderate in severity.

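### Section 4.6.2 makes any-grade myocarditis a mandatory stop, but Appendix 9, Table 6 tells sites to resume atezolizumab when a Grade 2 event resolves

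*Protocol*

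**What the plan says.** Protocol Section 4.6.2 opens its list of stopping criteria with: "Patients must discontinue study treatment (but will continue to receive tumor assessments) if they experience any of the following". One item is "Myocarditis of any grade". The section contains a single exception, for radiographic progression: "Patients will be permitted to continue atezolizumab after RECIST v1.1 criteria for progressive disease are met", subject to conditions on clinical benefit. Nothing comparable is attached to myocarditis, and the section does not refer to Appendix 9.

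Appendix 9 introduces its myocarditis table with a direction: "Patients with signs and symptoms of myocarditis, in the absence of an identified alternate etiology, should be treated according to the guidelines in" Table 6. The Grade 2 row of Table 6 then says:

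- "Withhold atezolizumab for up to 12 weeks after event onset", with Medical Monitor contact;
- "If event resolves to Grade 1 or better, resume atezolizumab" (footnote b requires a steroid taper first, if steroids were started);
- "If event does not resolve to Grade 1 or better while withholding atezolizumab, permanently discontinue atezolizumab and contact Medical Monitor".

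The Grade 3–4 row requires permanent discontinuation. Footnote c is attached to that row and to the unresolved Grade 2 line: "Resumption of atezolizumab may be considered in patients who are deriving benefit and have fully recovered from the event". It requires documented approval by both the investigator and the Medical Monitor. The opening text of Appendix 9 has the same clause for all permanent discontinuations.

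Section 5.1 sends sites to Section 5.1.2, Appendix 9 and the Investigator's Brochure for interruption and discontinuation criteria. It does not mention Section 4.6.2.

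**The concern.** Two current provisions of the same protocol give opposite default instructions for the same patient. If Grade 2 immune-related myocarditis settles to Grade 1 or better within the holding period, Section 4.6.2 says treatment has ended and Table 6 says to restart it.

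A site treating an acute cardiac event will probably open the event-specific table, because Section 5.1 points there and Appendix 9 says such patients should be managed by it. A site that follows Table 6 faithfully would redose a patient whom a mandatory rule says must stop, and might not know it had breached the protocol. The toxicity is potentially life-threatening: the Grade 2 row itself raises temporary pacing and mechanical circulatory support as options. The stake is re-exposure of a patient, together with an avoidable protocol breach.

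**Working it through.** No arithmetic applies. The documents give no myocarditis incidence, and the point depends on no sample size or event count. The check is a comparison of the two rules by grade.

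| Myocarditis event | Section 4.6.2 | Appendix 9, Table 6 | Result |
|---|---|---|---|
| Grade 1 | Stop | No row | Table silent; no opposing instruction |
| Grade 2, resolves to Grade 1 or better | Stop | Hold, then resume | **Direct conflict** |
| Grade 2, does not resolve | Stop | Hold, then permanent stop | Same end point |
| Grade 3–4 | Stop | Permanent stop | Same |

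Four readings that might remove the conflict were then tested.

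1. *Do the rules cover different patients?* Table 6 is limited to immune-related myocarditis, while Section 4.6.2 covers all myocarditis. The narrower set lies inside the wider one, so a Grade 2 immune-related event is subject to both.

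2. *Does discontinuing in Section 4.6.2 mean pausing?* Section 5.1.2 distinguishes temporary suspension from discontinuation of study drug. The Section 4.6.2 list also includes pregnancy and use of another systemic anti-cancer therapy, and it asks for a discontinuation reason on the eCRF. A pause does not fit that list.

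3. *Is the Grade 2 resume line just an instance of approved re-challenge after a stop?* No. Re-challenge requires full recovery, evidence of benefit and documented approval by two parties. The Grade 2 resume line requires resolution to Grade 1 or better and, where relevant, the steroid taper. It makes resumption the default.

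4. *Does any text rank the two?* None was found in the protocol or SAP. Sections 4.3.2, 5.1 and 5.1.2 lead the reader towards Appendix 9 without ranking it against Section 4.6.2. The only indication is the wording: Section 4.6.2 says *must*, while Appendix 9 offers guidelines that *should* be followed.

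The conflict survives all four readings, in one row of one table.

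**The case against.** The strongest defence is that the two texts do not carry equal force. A mandatory stop in the protocol body would ordinarily prevail over guidance in an appendix, so a site that stops is on safe ground. The sponsor should also know of the case before any redose: Section 5.2.3 makes Grade 2 or higher myocarditis reportable within 24 hours, and the Grade 2 row itself requires Medical Monitor contact. Both points stand, and they lower the practical risk. They do not remove the conflict, because neither tells the site or the Medical Monitor whether redosing is permitted, and the table still instructs it.

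Three stronger inferences are tempting, and the documents do not support them.

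- *That the re-challenge provisions also contradict Section 4.6.2.* Section 4.6.2 is silent on later resumption; it does not forbid it. A stop followed by approved resumption is this protocol's usual structure. Section 5.1.2 allows resumption with Medical Monitor agreement after a patient has been discontinued for a hold beyond 12 weeks. Appendix 9's own all-grade stops, for myasthenia gravis, Guillain-Barré syndrome and meningoencephalitis, carry the same re-challenge footnote. This is a gap worth clarifying.
- *That Section 9.2 leaves sites unable to resolve the matter.* It bars prospective requests to deviate. Asking which of two provisions applies is a request for clarification.
- *That the analyses are affected.* The choice of rule does not change whether the myocarditis itself counts towards the primary endpoints. In SAP Section 3.5.3, the table combining discontinuation and interruption would include a Grade 2 case under either rule. Any movement in the discontinuation-only, exposure or deviation summaries would be negligible.

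**Conclusion.** The point holds as an internal inconsistency in the current protocol text. For Grade 2 immune-related myocarditis that resolves to Grade 1 or better, Section 4.6.2 requires a stop and Table 6 instructs resumption. The protocol and SAP do not say which governs, although the wording favours Section 4.6.2.

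Its reach is narrow. The default action differs only in that one situation, and no frequency can be given because the documents supply no rate. It still warrants correction: it concerns a stopping rule for a serious toxicity, and the cost of aligning the texts is very small.

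The conclusion rests on two things. First, discontinuation in Section 4.6.2 is read as ending treatment, for the reasons set out above. Second, the absence of a ranking is established only for the protocol and SAP; Sections 5.1 and 5.1.2 also refer to the Investigator's Brochure, which was not available for this review.

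**What to change.** Change the Grade 2 row of Appendix 9, Table 6 to permanent discontinuation of atezolizumab with Medical Monitor contact, so that it matches Section 4.6.2. The protocol does not state the sponsor's intent. Aligning to the mandatory and stricter text is the safer direction, and the sponsor should confirm it when making the change.

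Until the amendment is approved under Section 9.6, send sites a clarification that only restates the existing Section 4.6.2 stop. It should not introduce a new bar on re-challenge, because that would be a change needing its own approval.

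Optionally, state in Section 4.6.2 whether the approved re-challenge clause in Appendix 9 (the general text and Table 6, footnote c) applies after myocarditis.

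The cost is one table row in the next amendment, with its usual ethics and regulatory approvals, and one letter to sites. The clinical downside is that a few patients whose Grade 2 event has resolved would lose resumption as the default option. There is no statistical cost.
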